## PRÉCIS

### Background:

- Most men diagnosed with prostate cancer will present with intermediate or high-risk disease.
- Many develop castrate resistant prostate cancer (CRPC) as curative strategies are often unsuccessful.
- Treatment options typically involve radical prostatectomy (RP) or radiation therapy (RT) in combination with androgen deprivation therapy (ADT).
- Even when cancers are initially sensitive to ADT, resistance ultimately emerges either through clonal selection or through a variety of adaptive mechanisms (secondary resistance).
- The recent introduction of novel androgen pathway inhibitors offers an opportunity to potentially improve the cure rate of men with intermediate and high risk localized prostate cancer.
- There remains a great need for improved techniques to determine mechanisms of treatment response and resistance.

### Objectives:

- To test the feasibility of multi parametric magnetic resonance imaging (mpMRI) for the localization and detection of focal prostate cancer both before and after pre-operative treatment with ADT and enzalutamide.

### Eligibility:

- Patients with nonmetastatic castration sensitive prostate cancer with intermediate or high-risk features
- Patients with testosterone levels  $\geq 100$  ng/dL
- ECOG 0-1

### Design:

- Patients will be treated with ADT and enzalutamide for 6 months
- Two 3T mpMRI endorectal examinations (One at screening and after 6 month of treatment)
- Screening biopsy (MR/US guided) samples
- Standard of care prostatectomy (RP) following post treatment mpMRI
- All tumor specimens will undergo genomic analysis

## STATEMENT OF COMPLIANCE

The trial will be carried out in accordance with International Council on Harmonisation Good Clinical Practice (ICH GCP) and the following:

- United States (US) Code of Federal Regulations (CFR) applicable to clinical studies (45 CFR Part 46, 21 CFR Part 50, 21 CFR Part 56, 21 CFR Part 312, and/or 21 CFR Part 812)

National Institutes of Health (NIH)-funded investigators and clinical trial site staff who are responsible for the conduct, management, or oversight of NIH-funded clinical trials have completed Human Subjects Protection and ICH GCP Training.

The protocol, informed consent form(s), recruitment materials, and all participant materials will be submitted to the Institutional Review Board (IRB) for review and approval. Approval of both the protocol and the consent form must be obtained before any participant is enrolled. Any amendment to the protocol will require review and approval by the IRB before the changes are implemented to the study. In addition, all changes to the consent form will be IRB-approved; an IRB determination will be made regarding whether a new consent needs to be obtained from participants who provided consent, using a previously approved consent form.

## INTRODUCTION

### 1.1 STUDY OBJECTIVES

#### 1.1.1 Primary Objective

- To test the feasibility of mpMRI for the localization and detection of focal prostate cancer both before and after pre-operative treatment with ADT and enzalutamide.

#### 1.1.2 Secondary Objectives

- To perform parallel sequencing of each unique tumor focus in the prostate before and after treatment with ADT and enzalutamide to determine the genetic predictors of primary resistance. (This will be done both inter-patient and intra-patient.)
- To determine the quantitative and qualitative mpMRI characteristics of response both before and after treatment, to predict resistance to intensive androgen targeted therapies and link imaging to genomic characterization of resistance.
- To evaluate the pathological complete response rate after neoadjuvant treatment with ADT and enzalutamide.

### 1.2 BACKGROUND AND RATIONALE

It is expected that 29,480 men will die from prostate cancer in the US in 2014.[\[1\]](#) The majority of these men will present with intermediate or high risk localized cancer. While some of these men are cured, many men (20 – 40% of those diagnosed) will ultimately develop castrate resistant prostate cancer (CRPC) and succumb to the disease.[\[2\]](#) Treatment options typically involve radical prostatectomy (RP) or radiation therapy (RT) in combination with androgen deprivation therapy (ADT). Following RP upwards of 50% of patients with high-risk disease will experience a biochemical recurrence at 5 years,[\[3\]](#) and approximately 20% will die of their disease in 10-15 years.[\[4\]](#)

**Abbreviated Title:** Neoadjuvant ADT & Enzalutamide

**Version Date:** 01/25/2024

ADT interferes with androgen production or blocks androgen at the level of the androgen receptor (AR).[\[5\]](#) As a consequence prostate cancer growth is suppressed and apoptosis occurs. There is great variability in prostate cancers' sensitivity to ADT and the mechanism of induction of apoptosis when it occurs is poorly understood. Some tumors appear to exhibit primary resistance, meaning the tumor persists despite ADT. Even when cancers are initially sensitive to ADT, resistance ultimately emerges either through clonal selection or through a variety of adaptive mechanisms (secondary resistance).[\[6\]](#) Thus, the duration of long-term response to ADT is unpredictable. Due to the lack of *in vivo* markers of tumor response it has not been possible to predict either the inherent cellular properties of resistance (primary resistance) or the timing of conversion to castration resistance prostate cancer (secondary resistance).

The recent introduction of novel androgen pathway inhibitors offers an opportunity to potentially improve the cure rate of men with intermediate and high risk localized prostate cancer but has also creates a need for improved techniques to determine mechanisms of treatment response and resistance. It is this challenge that we seek to address in this clinical trial by linking pathologic tumor response to both genomics and imaging to predict androgen resistance. We will examine the response of tumors to goserelin and enzalutamide in the preoperative setting.

### **1.2.1 Preliminary experience with ADT prior to prostatectomy**

In a previous study, the 17  $\alpha$ -hydroxylase/C17,20 lyase inhibitor abiraterone +ADT prior to prostatectomy yielded rapid PSA declines (including near or complete responses), however approximately two-thirds of studied patients demonstrated little or no tumor shrinkage.[\[7\]](#) This suggests that primary resistance to even modern anti-androgen therapy remains a formidable challenge. Several mechanisms of resistance to ADT have been identified, including persistent ligand and androgen receptor mutation.[\[6, 8\]](#) Despite this, the genomic determinants of resistance to ADT remain incompletely characterized. The extent to which such mechanisms might generalize across ADT regimens (such as ADT + Enzalutamide) or operate in specific therapeutic contexts also remains unknown.

### **1.2.2 Rationale for Enzalutamide in the Neoadjuvant Setting**

The clinical importance of enzalutamide in the treatment of prostate cancer is likely just emerging. Given its ability to improve survival (in both chemotherapy-naïve patients and patients who have already received docetaxel), its relative lack of toxicity, and no requisite prednisone, there is increasing interest to use this treatment earlier in the disease process. One possible therapeutic strategy could employ enzalutamide in the neoadjuvant setting. It would be interesting to determine if enzalutamide can induce a complete pathologic response in some patients, or significantly shrink tumors (identified via endo-rectal MRI) in other patients. Associations with these pathologic and/or radiographic changes and delayed recurrence or cure could drive additional studies in the future with clinical endpoints.

### **1.2.3 Possible Mechanisms of Resistance in Prostate Cancer**

There are multiple mechanisms of resistance that have been proposed in prostate cancer, but it remains unclear which are most prevalent and relevant in newly diagnosed patients. In treatment naïve patients it is most likely that signaling within the androgen receptor pathway drives prostate cancer cellular proliferation. Therefore AR over expression at baseline, via amplified gene expression or increased molecular stability, may be one mechanism of resistance.[\[9, 10\]](#)

Molecular changes in the AR such as AR splice variants could enhance ligand-independent AR signaling and lead to primary drug resistance.[\[6\]](#) Enhanced efficacy of intranuclear steroid receptors functioning downstream from the AR could serve as coactivators for transcription, promoting treatment resistance. In addition, prostate cancer cells may utilize autocrine- or paracrine-mediated cellular growth, producing various androgens to drive these aberrant mechanisms through cytochrome P17 (CYP17)-mediated androgen synthesis.[\[11, 12\]](#) Additional possible mechanisms include AR signaling cascades that have been associated with cellular proliferation and decreased apoptotic activity.[\[13\]](#)

#### 1.2.4 Understanding Resistance Patterns

Broadly, several hypotheses may explain genetic resistance to ADT (**Table 1**):

- I. Positive selection for intrinsic clonal or subclonal resistance effectors present within heterogeneous tumors,
- II. Acquisition of new resistance effectors as a result of therapy, or
- III. Adaptive cellular responses (e.g., feedback mediated up-regulation of bypass pathways).

**Table 1. Potential resistance effectors and approaches for discovery.**

Putative Resistance Mechanism	Sequencing Platform Discovery	Proposed Computational Solution
Tumor heterogeneity	Whole genome sequencing	Assess clonal and subclonal driver alteration selection
Selection for tumor suppressor losses or oncogene amplification	Whole genome	Assess for clonal and subclonal copy gains and losses
Acquisition of new variants	Whole genome sequencing	Identify acquired driver alterations
Adaptive cellular response	Transcriptome	Identify longitudinal alteration and expression changes

A goal of this proposal is to systematically interrogate these potential resistance mechanisms by computationally identifying in genomic resistance effectors to ADT in the preoperative setting. Previous studies have utilized massively parallel sequencing technologies to define the spectrum of somatic events occurring in primary and metastatic prostate cancer.

**Abbreviated Title:** Neoadjuvant ADT & Enzalutamide

**Version Date:** 01/25/2024

[figure not shown]
[14-16] These studies have identified multiple genomic events that may contribute to prostate oncogenesis.

### 1.2.5 Preliminary studies for prostate Multiparametric 3T prostate magnetic resonance imaging guided prostate biopsy

Recent literature supports the contention that Multiparametric 3T prostate magnetic resonance imaging (mpMRI) has high specificity for the detection of focal prostate cancer. [17] Multiparametric techniques are a combination of morphologic and functional sequences. These mpMR exams include diffusion (DWI), contrast enhanced (DCE) and T2W sequences. This combination allows for a detailed assessment of focal cancers, based upon cellularity (DWI), perfusion (DCE), neovascularity (DCE) and cell density (T2W). Many studies have demonstrated the increased specificity for *in vivo* cancer detection, diagnosis, tumor volume and most importantly the ability to differentiate aggressive (Gleason 4 or greater) from the indolent (Gleason 3 or less) cancer. [17, 18] Each of the individual sequences T2W, diffusion (DWI) and dynamic contrast enhanced (DCE) have been tested and validated both individually and in combination. A recent study done here at the NCI reported positive predictive values of 98%, 98% and 100% for whole gland, peripheral zone and central gland lesions respectively and like other studies also suggest it is more accurate for focal lesions over 0.5 cm and for higher Gleason grade lesions.[17] As [name] et al have also shown, using ROC analysis the AUC value for MRI volume estimates of tumors over 0.5cm^3 is 0.95. [19]

### 1.2.6 MR-US prostate Biopsy

The MR-US “fusion” approach pioneered by Drs. [name] and [name] can be used to specifically biopsy lesions seen on mpMRI. Such targeted biopsies will be evaluated in the men prior to neoadjuvant anti-androgen therapy. All men will have a 3T MR examination and MR/US fusion guided biopsy will utilize custom biopsy probe with the embedded passive electromagnetic (EM) tracker that allows real-time tracking of the US image and needle location. 3D reconstructed US volume will be registered and fused with the pre-biopsy MRI dataset. Continuous correction of rigid motion between the reconstructed reference 3D US volume and real-time 2D US images will enable tracking of the target lesions over the course of the biopsy procedure. The technical aspects and validation of this approach have been described earlier.[20] Biopsy targets identified in the MRI and re-identified in TRUS by means of registration will be sampled under real-time US guidance. The EM tracking and fusion technology we plan to use for this procedure has been developed and thoroughly validated by the NCI, and has been applied in more than 195 cases. [21, 22]

[figure not shown]
**Abbreviated Title:** Neoadjuvant ADT & Enzalutamide

**Version Date:** 01/25/2024

Figure 1: Cancer detection rates comparing 12 core TRUS and MR/US biopsy based upon MR suspicion level.

[figure not shown]
**Custom made patient –specific MR based prostate gland molds:** A 3D model of the prostate can be created in a novel technique developed and pioneered in the Clinical center ([Figure 2](#)), as described previously.[\[23\]](#) In brief it is a 3D model based upon MR images, which begins with manual segmentation of the MR T2W images. The prostate is outlined and converted via software into a 3D object. This is then imported into SolidWorks (SolidWorks, Dassault Systèmes SolidWorks Corp., Concord, MA, USA). There it is subtracted to create an internal cavity that precisely shapes the patients' gland. Slots for slicing the gland at 6mm intervals are designed and orientation markings (Superior/Inferior, Right/Left etc.) are added and it is then created using a 3D printer.

Figure 2: Customized, patient-specific prostate specimen mold. (a)Three-dimensional representation of final prostate mold in green, shown in two halves with a 3D model of the patient's prostate shown in brown. (b) Mold is created using a 3D printer, shown here in two halves fit together using small pegs/slots in the corners.

The mold approach has also been shown to allow for decision system support development [\[24\]](#) that provides a probability map of peripheral zone cancers based upon MRI. This expertise will be critical to the imaging, allowing suspicious lesions to be targeted for biopsy and subsequent correlative genetic analyses to be performed on the tissue from the index lesion(s). This unique tool allows for the most accurate alignment of the prostate specimen to MR images that is available today. This resource available here at the NCI will be essential for the success of this proposal allowing for precise validation of in vivo imaging studies by enabling registration for focal lesion core biopsy and whole mount histopathology.

Figure 3: Digitized multiparametric MRI maps (left) and the corresponding digitized whole-mount histopathology (right) slice with tumor outlined by a prostate cancer pathologist, and used as a landmark for lesion confirmation on mp MRI maps determine lesion localization.

### 1.2.7 Summary

Patients will be treated with goserelin and enzalutamide prior to RP. Learning what molecular profile is associated with resistance to intense anti-androgen therapy and linking this to predictive information from imaging will provide critical insight into the biology of prostate cancer and help develop predictive markers for potentially curative therapy. We will define the corresponding roles of imaging and genomics before and after treatment with goserelin and enzalutamide in men on this clinical trial

A complex but central prostate cancer research problem, the unpredictable resistance to ADT in high risk prostate cancer, is addressed in this study. There is currently no way to detect early resistance to ADT. As the common pathway for lethal prostate cancer is resistance to ADT, prediction and visualization of resistance to ADT through imaging and genomic markers would be a major advance for all men with this phenotype. It will allow quantification and characterization of the residual cancer burden (RCB) and this knowledge if predictive of long-term tumor response will allow real-time stratification of patients to the most effective therapy.

The advent of targeted therapies, exemplified by immunotherapy agents, creates new complexities in the assessment of response. There is increasing need for imaging modalities which can accurately and reproducibly measure not just change in tumor size, but changes in relevant metabolic parameters, modulation of relevant signaling pathways, drug delivery to tumor, and differentiation of apoptotic cell death from other changes in the tumor volume. Our studies here at the NCI have previously developed *three unique contributions* to the imaging and image guided diagnosis of prostate cancer, namely validated quantitative mpMR, MR-ultrasound guided biopsy techniques and mapping of tumor loci from MRI to prostatectomy specimen, by custom designed 3D molds.

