**Table 2: Clinical Protocol Procedures**

At prostatectomy, the fresh prostate gland will be processed. The custom-made 3D mold, created for the individual patient with MRI data, will be used to guide placement of the “post treatment biopsy”, which is actually a sampling of the prostatectomy specimen in the exact geometric location as the pre-treatment biopsy. The fresh prostatectomy specimen will be placed in the mold and the one or two core samples obtained will be handled as described above. Documentation of precise location of the biopsy will be recorded with appropriate coordinates, and location will be correlated with the subsequent cutting of tissue cross sections. Then, the tissue will be processed by NCI Laboratory of Pathology staff for diagnosis and pathology report generation. The cross sections will be labeled and will be cut into halves or quadrants for routine histology processing, while documenting which cross section and quadrant (right anterior #1, left posterior #1, etc.) from which they originated. This will serve as a guide to the location of the post treatment biopsy, as that location will have been recorded keeping in mind the cross section number. After the prostatectomy specimen has been signed out by the Pathology Department

with final diagnosis and report issued, correlation between the post treatment biopsy and the whole section will occur. The tissue section(s) from which the post treatment biopsy was taken will be analyzed morphologically and compared to the biopsy. If indicated, the block or blocks of the slides to be compared can be sectioned further for complete morphologic analysis of presence/absence of residual tumor, tumor grade, tumor extent, etc.

MR 2 data will be performed according to the specialized protocol reported previously. [17, 23] All tumor foci will be re-identified. The 3D mold will provide target localization and trajectory path for post prostatectomy core biopsies.

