## **STATISTICAL CONSIDERATIONS**

The primary objective of this exploratory trial is to obtain pilot data to assess the utility and role of mpMRI in localization and detection of focal prostate cancer both before and after treatment with pre-operative ADT and enzalutamide. Secondary objectives include obtaining pilot data to guide future studies with respect to determining genetic predictors and correlates of response to therapy as well as to link imaging information to genomic information related to resistance.

Patients who have newly diagnosed prostate cancer will undergo treatment with androgen deprivation therapy and enzalutamide and will undergo mpMRI imaging at screening and 6 months. The imaging will be used to monitor the changes in the individual tumors located within the prostate. As these patients will all have multiple tumors within the prostate, it is anticipated that approximately 25% of the patients will experience minimal declines in tumor and still have significant residual disease, 25% may have complete disappearance of tumor, and the remainder will show substantial improvement (disappearance of some lesions, with others being much smaller). To guide sample size determination, it is estimated that for an exploratory investigation of the association of genomic information and its relationship to response, it would be useful to have at least a minimum of 10 patients who still have significant residual disease in order to form preliminary assessments of the relationships noted. As such, if 50 total evaluable patients were to enroll on the trial and if the probability of being in this category was 25%, there would be 83.6% probability of having at least 10 such patients. Thus, this pilot study will plan to enroll 50 total evaluable patients who would all undergo primary treatment and mpMRI imaging to assess the role of imaging in this setting. The accrual ceiling will be 55 in order to accommodate a small number of patients who may be inevaluable. Successful use of this imaging will lead to analyses related to the association with genomic traits at baseline and prostatectomy and whether there is disappearance of tumor or not. On this trial, all of these investigations will be performed with exploratory, hypothesis generating intent.

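### Section 8 expects three grades of response and sizes the trial on the worst one, but words the genomic association as tumor disappearance yes/no, which merges that group with the substantial responders

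*Combined protocol and SAP*

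**What the plan says.** The Statistical Considerations (Section 8 in the table of contents) describe three grades of response. The first: "approximately 25% of the patients will experience minimal declines in tumor and still have significant residual disease". The other two: "25% may have complete disappearance of tumor, and the remainder will show substantial improvement (disappearance of some lesions, with others being much smaller". The middle share is therefore 100 − 25 − 25 = 50%.

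The sample size rests on the first group. For an exploratory look at genomics and response, "it would be useful to have at least a minimum of 10 patients who still have significant residual disease". The supporting probability, 83.6%, is given for the case "if 50 total evaluable patients were to enroll on the trial and if the probability of being in this category was 25" percent.

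The same section then states the form of the association: "association with genomic traits at baseline and prostatectomy and whether there is disappearance of tumor or not". It gives no test, alpha, effect size or trait frequency, and calls all of this work exploratory.

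Three other places bear on the point:
- The secondary objectives (Section 1.1.2) cover genetic predictors of primary resistance, quantitative and qualitative mpMRI response linked to genomics, and the pathological complete response rate.
- The Summary in Section 1.2.7, which is background, says "It will allow quantification and characterization of the residual cancer burden (RCB". The term appears nowhere else.
- Histopathological Analysis (5.1.1 in the contents, 1.17.1 in the text) has the sections that yielded the post-treatment core examined and compared with it. Where indicated, further sectioning is allowed for "complete morphologic analysis of presence/absence of residual tumor, tumor grade, tumor extent, etc".

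**The concern.** The trial looks for predictors of primary resistance, and the men who show resistance most clearly are those with significant residual disease. They are the reason for enrolling 50. A response variable cut at disappearance gives them the same value as men whose tumor shrank greatly. A trait that moves men from substantial improvement to significant residual disease, without changing who clears the tumor, cannot be seen in that analysis at all.

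With about 50 men, information per man is what the pilot has least of. An ordered response uses grades that Section 8 already describes. If the choice is left open until the data are in, the response cut can also be picked after the fact.

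**Working it through.** **1. The plan's own figure.** With X ~ Binomial(50, 0.25), P(X ≥ 10) = 0.8363, which reproduces the stated 83.6%.

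**2. What the yes/no cut merges.** Expected counts in 50 men are 0.25 × 50 = 12.5 with significant residual disease, 0.50 × 50 = 25 substantially improved and 12.5 with no tumor. The association as worded compares 12.5 men with 12.5 + 25 = 37.5. One third of the larger group (12.5 / 37.5) is the group on which the sample size was set.

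**3. Information kept.** Assume a normal latent burden (not in the documents). Let p = 0.25, with normal quantile −0.674 and density φ = 0.318.
- Yes/no against a continuous burden: φ² / [p(1 − p)] = 0.101 / 0.1875 = 0.539.
- Three grades 25/50/25 against a continuous burden: 2 × 0.25 × (φ / 0.25)² = 0.808.
- Burden graded above zero, with the lowest 25% tied at zero, against a continuous burden: 0.940.
- Hence yes/no against the zero-tied graded burden: 0.539 / 0.940 = 0.573. Yes/no against three grades: 0.539 / 0.808 = 0.667.

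The yes/no outcome thus keeps about 54 to 57% of the information in a graded burden. At 0.573, 50 men analyzed yes/no are worth about 0.573 × 50 ≈ 29 men analyzed on the graded scale.

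**4. In terms of power.** At two-sided 0.05 (assumed), 80% power corresponds to a standardized effect of 1.960 + 0.842 = 2.802. Yes/no power is Φ(2.802 × √e − 1.960), where e is the fraction of information kept. The result is 0.54 for e = 0.539, 0.56 for e = 0.573 and 0.63 for e = 0.667.

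**5. Simulation at n = 50.** There were 4,000 runs per setting. The lowest 25% were tied at zero, and the trait shifted burden by 1 SD. A rank-sum test was used for the three grades and the graded burden. Trait prevalence and shift are assumptions.

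| Trait prevalence | Direction | Yes/no, Fisher | Yes/no, chi-square | Three grades | Graded burden |
|---|---|---|---|---|---|
| 20% | raises burden | 0.222 | 0.294 | 0.692 | 0.756 |
| 30% | raises burden | 0.408 | 0.504 | 0.799 | 0.850 |
| 50% | raises burden | 0.576 | 0.724 | 0.874 | 0.917 |
| 20% | lowers burden | 0.575 | 0.611 | 0.672 | 0.713 |
| 30% | lowers burden | 0.674 | 0.712 | 0.802 | 0.850 |

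A separate run at 30% prevalence gave, in the same column order, 0.41, 0.48, 0.79 and 0.86 (raises) and 0.65, 0.70, 0.79 and 0.84 (lowers).

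**6. How much the three grades recover.** At 30% prevalence with burden raised, they recover (0.799 − 0.504) / (0.850 − 0.504) = 85% of the gap from chi-square to the fully graded burden.

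**The case against.** The strongest reply is that the concern reads one sentence too narrowly. Section 8 itself sets out the three grades and ties the residual-disease group to genomics and response, and Section 1.1.2 links quantitative mpMRI response to genomics both between and within patients. A graded analysis may be what the investigators intend, and lesion-level information is not in the simulation. This is fair. However, the only sentence that states the response variable is the yes/no one, and Section 1.20 says there will be no formal radiographic response assessment. If the residual-disease group against the rest were the intended outcome, power in the 30%, raised-burden case would be 0.64 by Fisher. That is better than 0.41 but still below the ordered analysis.

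A reader might infer from Section 1.2.7 that the trial promises a pathologic residual cancer burden score and fails to measure it. The documents do not support that. The sentence is background and most naturally refers to a future imaging and genomic capability. It does not call the measure pathologic or an endpoint. Nor is residual tumor left unmeasured: cores are read for grade and extent, the biopsied sections are examined morphologically, a full pathology report is issued, and T2, ADC and DCE metrics are recorded for every focus at both time points. What is missing is one defined graded response per man and its use in the analysis.

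Part of the Fisher gap is test conservatism. Its null rejection rate was 0.031, against 0.050 for the rank-sum test, so the chi-square column is the fairer comparison.

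**Conclusion.** The point holds. Section 8 describes an ordered response, bases 50 men on its worst grade, and then states an analysis in which that grade has no place of its own. An ordered analysis is a better method, built on grades the plan already has.

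The size depends on the direction of the effect. It is largest for resistance traits, which the trial most wants to find, and modest for traits that favor complete response. A reader might infer that about half the power is lost in general. The figures do not bear that out. At 30% prevalence with burden raised, the relative loss against the graded burden is 1 − 0.408 / 0.850 = 52% by Fisher and 1 − 0.504 / 0.850 = 41% by chi-square. With burden lowered it is 1 − 0.674 / 0.850 = 21% and 1 − 0.712 / 0.850 = 16%. Over all settings tried (prevalence 20 to 50%, shifts of 0.5 to 1.2 SD either way) it ran from about 10% to about 73%.

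Normal latent burden, alpha, prevalence and shift are all assumptions, and burden is taken as measured without error. The trial is exploratory and states no power for this association. The consequence is therefore lost precision in a pilot meant to guide later studies, not a broken design claim.

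**What to change.** In Section 8, make the ordered response the response variable for the baseline genomic and baseline mpMRI associations: no tumor, substantially reduced, significant residual tumor. Write down how each man is assigned a grade before the associations are examined. Where residual tumor extent from the prostatectomy pathology is recorded, it can be used instead, with zero for none. Analyze by a rank test or a proportional-odds model. Keep disappearance yes/no as a descriptive summary.

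In Section 1.2.7, either define residual cancer burden as this measure or drop the term.

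The cost is some SAP wording, a little more analysis and one graded response per man for about 50 men. It needs no extra patients, tissue or procedures. A score such as tumor area times cellularity is optional, and it would not be free. The Figure 3 caption mentions "the corresponding digitized whole-mount histopathology (right) slice with tumor outlined by a prostate cancer pathologist", but that is background. No procedure requires outlining or digitizing every gland, and the histology text has cross sections cut into halves or quadrants. Since the three grades recover most of the gain, the change does not depend on that extra pathology work.
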